**Investigational Product(s):**

Enzalutamide 40 mg capsule

**Dose(s):**

160 mg once daily

- CONFIDENTIAL -

Mode of Administration: Oral, with or without food

Comparative Drug(s): Placebo capsules that are identical in appearance to enzalutamide will be administered in the same manner and frequency as enzalutamide.

Enzalutamide Dose Reduction / Dose Adjustment Subjects who experience a grade 3 or higher toxicity that is attributed to the study drug and cannot be ameliorated by the use of adequate medical intervention and/or dose reduction may interrupt study drug treatment for 1 week or until the toxicity grade improves to grade 2 or lower in severity. Study drug may be restarted at the original dose (160 mg/day) or a reduced dose (120 mg or 80 mg/day). If restarted at a lower dose or if interrupted for > 2 weeks, the Medical Monitor must be consulted.

Other Treatment for Prostate Cancer during the Study: ADT (either bilateral orchiectomy or LHRH agonist/antagonist) will be maintained during study treatment. LHRH agonist/antagonist will be provided from the site's pharmacy stock and administered in accordance with the prescribing information.


Concomitant Medication Restrictions or Requirements: Required Concomitant Treatment All subjects will be required to maintain ADT during study treatment, either using an LHRH agonist/antagonist or having a history of bilateral orchiectomy. Prohibited Concomitant Treatments The following medications are prohibited within 4 weeks of day 1 and during the study treatment period:
 

• 5 <math>\alpha</math>-reductase inhibitors (finasteride, dutasteride);

• Estrogens;

• Cyproterone acetate, megestrol acetate;

• Biologic or other agents with antitumor activity against prostate cancer (with the exception of those therapies identified in exclusion criterion No. 1);

• Systemic glucocorticoids greater than the equivalent of 10 mg per day of prednisone intended for the treatment of prostate cancer;

• Herbal medications that have known hormonal antiprostate cancer activity and/or are known to decrease PSA levels (i.e., saw palmetto);

• Androgens (testosterone, dihydroepiandrosterone, etc.);

• Investigational agents.

 
In addition, bisphosphonates and denosumab are prohibited unless stabilized for 2 weeks prior to randomization and held constant, as tolerated, throughout study treatment or administered for diagnosis of osteoporosis.
 
Enzalutamide Drug Interaction There is a potential for enzalutamide to affect exposures to other medicinal products, or for other medicinal products to affect exposure to enzalutamide:
 

• Strong cytochrome P450 (CYP) 2C8 inhibitors (e.g., gemfibrozil) are to be avoided. If subject must be coadministered a strong CYP2C8 inhibitor, the dose of enzalutamide should be reduced to 80 mg once daily. If coadministration of the strong inhibitor is discontinued, the enzalutamide

- CONFIDENTIAL -

dose should be returned to the dose used prior to initiation of the strong CYP2C8 inhibitor.

- Strong CYP3A4 inducers (e.g., carbamazepine, phenobarbital, phenytoin, rifampin) or moderate CYP3A4 inducers (e.g., bosentan, efavirenz, etravirine, modafinil, nafcillin, St. John's Wort) should be avoided if possible as they may reduce enzalutamide plasma concentration if coadministered. Selection of a concomitant medication with no or minimal CYP3A4 induction potential is recommended.
- Enzalutamide is a strong inducer of CYP3A4 and a moderate inducer of CYP2C9 and CYP2C19. Medicinal products with a narrow therapeutic range that are substrates of CYP3A4 (e.g., alfentanil, cyclosporine, dihydroergotamine, ergotamine, fentanyl, pimozide, quinidine, sirolimus, tacrolimus), CYP2C9 (e.g., phenytoin, warfarin), or CYP2C19, or UGT1A1 (e.g., S-mephenytoin) should be avoided if possible, as enzalutamide may decrease their exposure.
- If enzalutamide coadministration with warfarin cannot be avoided, additional international normalized ratio (INR) monitoring should be conducted.
- Enzalutamide is an inhibitor of human P-glycoprotein (P-gp) and may increase exposure to medicines that are P-gp substrates. Medicinal products with a narrow therapeutic range that are substrates for P-gp (e.g., digoxin, colchicine, dabigatran etexilate) should be used with caution when administered concomitantly with enzalutamide.

#### *Permitted Concomitant Treatment*

The following treatments are allowed during the study (and do not require study drug discontinuation) including, but not limited to:

- Blood transfusions and growth factor support per standard of care and institutional guidelines;
- Steroid use (for indication other than prostate cancer) per standard of care;
- Pain therapy per standard of care and institutional guidelines;
- Palliative radiation therapy including external beam radiotherapy or systemic radionuclides (e.g., Samarium or Strontium);
- Vaccine therapy that has prior market authorization and is not intended to treat prostate cancer;
- Palliative surgical procedures to treat skeletal-related events.

Hormonal treatment for treating complications of LHRH analogue treatment (e.g., hot flashes) will be allowed with Medical Monitor approval. In addition, flutamide, bicalutamide or nilutamide are permitted only if given concurrently with LHRH agonist or antagonist to prevent flare (See [\[Appendix 12.9 Anti-Androgen Usage\]](#)).

#### **Duration of Treatment:**

Study drug should be continued as long as the subject is tolerating the study drug and until radiographic progression or starting another investigational agent or new therapy for treatment of prostate cancer.

#### **Discontinuation Criteria:**

Subject will be discontinued from the study drug treatment if any of the following occur:

- Any adverse event that is intolerable to the subject which cannot be ameliorated by the use of adequate medical intervention and/or dose reduction or that in the opinion of the investigator would lead to undue risk to the subject if dosing is continued.
- Subject who experiences a seizure or any condition that significantly predisposes the subject to seizure such as brain metastasis or clinically evident stroke.
- Subject who experiences a confirmed event of posterior reversible encephalopathy syndrome (PRES) by brain imaging, preferably by MRI.
- Subject initiates another investigational agent or new therapy for prostate cancer.
- Subject who has evidence of radiological disease progression as confirmed and in the judgment

- CONFIDENTIAL -

of the investigator is no longer deriving clinical benefit.

- Subject has discontinued ADT (LHRH agonist/antagonist) and has a testosterone value in the noncastrate range ( $> 50$  ng/dL).
- Dose interruptions  $> 14$  consecutive days. Dose interruptions for subjects who are deriving clinical benefit from treatment may be extended beyond 14 days after sponsor's approval. Dose interruptions of study drug  $\leq 14$  days consecutive are permitted at any point during treatment.
- Subject who is, in the opinion of the investigator or the Medical Monitor, noncompliant with the protocol requirements.
- Subject is lost to follow-up despite reasonable efforts by the investigator to locate the subject.
- Subject withdraws consent for the study.

Subject will be discontinued from the study follow-up (Safety or Long-term Follow-up) if any of the following occur:

- Subject is lost to follow-up despite reasonable efforts by the investigator to locate the subject.
- Subject withdraws consent for further follow-up.
- Death.
- Study termination by the Sponsor.

### **Endpoints for Evaluation:**

#### Primary Endpoints

- Time to PSA progression: PSA progression is defined as a  $\geq 25\%$  increase and an absolute increase of  $\geq 2$   $\mu\text{g/L}$  (2 ng/mL) above the nadir (i.e., lowest PSA value observed post baseline or at baseline), which is confirmed by a second consecutive value at least 3 weeks later. (Prostate Cancer Clinical Trials Working Group 3 criteria) (tested by central laboratory)

#### Secondary Endpoints

- rPFS
- Time to first SSE
- Time to castration resistance
- PSA response ( $\geq 50\%$ )
- PSA response ( $\geq 90\%$ )
- Time to initiation of new antineoplastic therapy
- PSA undetectable rate ( $< 0.2$  ng/mL)
- ORR

#### Exploratory Endpoints

- Time to deterioration of QoL
- Time to pain progression

#### Safety Endpoints

- Nature, frequency and severity of adverse events
- Safety laboratory tests: biochemistry and hematology
- Physical examination
- ECG
- Vital signs (blood pressure, pulse and temperature)

### **Statistical Methods:**

#### **Sample Size Justification:**

- CONFIDENTIAL -

The study is planned to randomize approximately 180 subjects (120 subjects in enzalutamide + ADT arm and 60 subjects in placebo + ADT arm, with 10% dropout) in order to observe at least 75 PSA progression events as planned for the final analysis. The sample size calculation is based on the following considerations:

A target hazard ratio (HR) is 0.50. The expected median TPP for the ADT arm is 9 months as measured from the date of randomization. A target HR of 0.50 corresponds to a 100% increase in median TPP for the enzalutamide plus ADT arm relative to the placebo plus ADT arm (approximately 18 versus 9 months).

The planned 75 PSA progression events provides approximately 80% power to detect a target HR of 0.50 based on a 2-sided log-rank test and overall significance level of 0.05. This assumed a recruitment period of 15 months and a follow-up period of 12 months.

There are 2 planned analyses, one final analysis at the total planned 75 PSA progression events and one interim analysis at 80% of the total planned events (about 60 PSA progression events providing 61% power to demonstrate superiority at a 2-sided alpha of 0.0244). TPP will be formally tested at both interim analysis and final analysis at 2-sided 0.0244 and 0.0429 significance level, respectively, for efficacy according to the O'Brien-Fleming boundary as implemented by Lan-DeMets alpha spending function. Data cut-off dates will be set when the planned number of events is reached for the interim and final analyses. If the exact number of events at interim and final analyses are different than planned, the significance level will be adjusted accordingly, based on the O'Brien-Fleming method with a Lan-DeMets alpha spending function. The family-wise type I error rate for this study is strongly controlled at 5% (2-sided) that allows the study to declare positive on primary endpoint TPP on the ITT population.

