### 7.1 Sample Size

As originally planned, approximately 180 Chinese subjects will be randomized in the study. (120 subjects in enzalutamide + ADT arm and 60 subjects in placebo + ADT arm).

The final analysis of TTPP will be conducted with a planned 75 PSA progression events based on the following considerations:

- A target HR is 0.5. The expected median TTPP for the ADT arm is 9 months as measured from the date of randomization. A target HR of 0.5 corresponds to approximately 100% increase in median TTPP for the enzalutamide plus ADT arm relative to the placebo plus ADT arm (approximately 18 versus 9 months, with 10% dropout rate).
- The planned 75 PSA progression events provides approximately 80% power to detect a target HR of 0.5 based on a 2-sided log-rank test and overall significance level of 0.05. PSA progression is defined as a  $\geq 25\%$  increase and an absolute increase of  $\geq 2 \mu\text{g/L}$  ( $2 \text{ ng/mL}$ ) above the nadir (i.e., lowest PSA value observed post baseline or at baseline), which is confirmed by a second consecutive value at least 3 weeks later. (Prostate Cancer Clinical Trials Working Group 3 criteria) (tested by central laboratory)
- There will be 1 interim analysis at 80% of the total planned events (about 60 PSA progression events), providing 61% power to demonstrate superiority at a 2-sided alpha of 0.0244.

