## 7.4 Analysis of Efficacy

### 7.4.1 Analysis of Primary Endpoint

#### 7.4.1.1 Primary analysis

Time to PSA progression (TTPP) is defined as a  $\geq 25\%$  increase and an absolute increase of  $\geq 2$  ng/mL above the nadir (i.e., lowest PSA value observed postbaseline or at baseline), which is confirmed by a second consecutive value at least 3 weeks later.

The effect of enzalutamide plus ADT compared to ADT will be tested using a stratified logrank test. The benefit of enzalutamide plus ADT compared to ADT will be summarized by a single HR with its 95% CI based on the Cox regression model. Kaplan-Meier curves will be used to estimate the distribution of the duration of time to PSA progression. Median duration of time to PSA progression will be estimated using the corresponding 50% percentile of the Kaplan-Meier estimates. A 2-sided 95% CI will be provided for these estimates.

There are 2 planned analyses, one final analysis at the total planned 75 PSA progression events and one interim analysis at 80% of the total planned events (about 60 PSA progression events). TTPP will be formally tested at both interim analysis and final analysis at 2-sided 0.0244 and 0.0429 significance level, respectively, for efficacy according to the O'Brien-Fleming boundary as implemented by Lan-DeMets alpha spending function [Lan-DeMets, 1983]. Data cut-off dates will be set when the planned number of events is reached for the interim and final analyses. If the exact number of events at interim and final analyses are different than planned, the significance level will be adjusted accordingly, based on the O'Brien-Fleming method with a Lan-DeMets alpha spending function. The family-wise type I error rate for this study is strongly controlled at 5% (2-sided) that allows the study to declare positive on primary endpoint TTPP on the ITT population.

- CONFIDENTIAL -

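### Do 15 months of recruitment plus 12 months of follow-up contradict the 75-event target?

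*Protocol*

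**What the plan says.** The Protocol Synopsis (Sample Size Justification) plans "120 subjects in enzalutamide + ADT arm and 60 subjects in placebo + ADT arm, with 10% dropout", and says this is done "in order to observe at least 75 PSA progression events as planned for the final analysis". The effect assumptions are "A target hazard ratio (HR) is 0.50" and "The expected median TPP for the ADT arm is 9 months as measured from the date of randomization". The timing sentence is "This assumed a recruitment period of 15 months and a follow-up period of 12 months". It does not say whether the 12 months run from the last randomisation or apply to each subject.

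Protocol 7.1 and SAP section 4 repeat the medians and the event target but omit both durations. On dropout, Protocol 7.1 has only "approximately 18 versus 9 months, with 10% dropout rate", with no time basis.

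The timing of the analyses is governed by events. Protocol 7.4.1.1 says: "Data cut-off dates will be set when the planned number of events is reached for the interim and final analyses". Protocol 7.8 and SAP 6.1.1.1 and 7.11 say the same. Neither document sets a minimum follow-up before a cut-off.

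**The concern.** A recruitment period followed by a follow-up period is usually read as accrual and then further observation after the last subject enters, here 27 months in all. On that reading 180 subjects produce far more than 75 events, so the cut-off rule would close the data well before month 27. Three consequences would seem to follow.

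- The event target, the sample size and the durations would not come from one calculation.
- The last subjects would have about 4 to 6 months of observation instead of 12. With scans at weeks 13 and 25, that is one scheduled post-baseline scan, or at most two. Radiographic progression-free survival, skeletal events, castration resistance and safety would be read on immature data.
- Interim and final analyses would fall only about 3 months apart, and the stated 80% would understate the power available at month 27.

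**Working it through.** **Inputs.** 120 and 60 subjects, HR 0.50, medians 18 and 9 months, 10% dropout, 15 and 12 months (Synopsis); interim and final levels 0.0244 and 0.0429 (Synopsis, Protocol 7.4.1.1). Exponential event times, uniform accrual and immediate detection are my assumptions. So are the readings of the dropout figure, because the documents give none.

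**1. The plan's own figures.** For 2:1 allocation, power = Φ(ln 2 × √(d × 2/9) − z).

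- d = 75, two-sided 0.05: Φ(2.830 − 1.960) = 0.808.
- d = 60, two-sided 0.0244: Φ(2.531 − 2.251) = 0.610.
- O'Brien-Fleming-type spending at information 0.8, with 0.025 in each tail, gives nominal levels of 0.0244 and 0.0429 and overall power of 0.800.

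All stated figures reproduce.

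**2. Reading A: 12 months after the last randomisation (T = 27).** With event hazard λ = ln 2/median, dropout hazard γ and k = λ + γ:

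P(event) = (λ/k) × [1 − (e^(−12k) − e^(−27k))/(15k)].

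The hazards are 0.0770 (placebo) and 0.0385 (enzalutamide) per month. Without dropout: 60 × 0.7647 + 120 × 0.5215 = 45.9 + 62.6 = 108.5 events.

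**3. Reading B: 12 months per subject.**

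P(event) = (λ/k) × [1 − e^(−12k)].

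Without dropout: 60 × 0.6031 + 120 × 0.3700 = 36.2 + 44.4 = 80.6 events.

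**4. Both readings across the dropout interpretations.**

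| Dropout reading | A: events at month 27 | A: month of 60th event | A: month of 75th event | B: events |
|---|---|---|---|---|
| None | 108.5 | 16.1 | 18.9 | 80.6 |
| 10% over 27 months | 105.1 | 16.3 | 19.2 | 78.9 |
| 10% per year | 101.1 | 16.5 | 19.6 | 76.9 |
| 162 evaluable | 97.6 | 17.3 | 20.6 | 72.5 |

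Under A the 75th event comes 27 − 20.6 = 6.4 to 27 − 18.9 = 8.1 months before month 27, and 3.9 to 5.6 months after the last randomisation. Under B the counts bracket 75.

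**5. Sensitivity of reading A.** Accrual weighted towards later months (density proportional to time) with 10% dropout per year gives about 94 events at month 27 and the 75th at about month 21.9. A one-month lag for detection or confirmation lowers the counts by about 3.

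**6. Power if the final analysis waited until month 27.** Using z = 2.025 (the 0.0429 level) at 98 to 108 events gives 0.89 to 0.92. That level belongs to looks at 60 and 75 events. With 0.0244 spent at 60 events, the final nominal level at 97.6 to 108.5 events is about 0.037 to 0.035, and the same single-look formula gives about 0.87 to 0.90. Either way this is a surplus over 80%.

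**The case for a change.** The best case for a change is that reading A is the ordinary one and the protocol's conduct fits it. No section stops observation at 12 months per subject: treatment runs to radiographic progression, and subjects who stop early stay on the PSA and scan schedule until progression or the required event count. If 10% dropout means 162 evaluable subjects, reading B gives 72.5 events, short of 75. Immature secondary data might also be hard to recover. Scheduled scans for subjects who stopped without progression end once the event target is met (Protocol 5.3.1.2), scans in the open-label phase are not collected (12.10.2), and the SAP censors radiographic progression-free survival before open-label treatment (6.1.2.1). A final cut-off at the later of 75 events and 12 months after the last randomisation would need no more subjects.

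What stands is that the follow-up period and the dropout basis are undefined, and that under reading A the secondary endpoints would be younger than a reader of the Synopsis might expect. What does not stand is the claim of an arithmetic contradiction: an unspecified term admits a reading under which the numbers agree. Nor is follow-up withheld, since the plan assumed a duration and never set a minimum. The 75 events are the number needed for power, worded as a floor. Expecting more than 75 is a margin against slow progression and against the events lost because samples after new therapy are not counted and unconfirmed rises are censored.

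The timing harm is also hypothetical. The planned study period runs from 3Q2019 to 4Q2025. The SAP (21 December 2022) and the current protocol (6 January 2023) both still describe the interim analysis as ahead, more than three years after the planned start. The documents give no accrual dates, so actual follow-up cannot be computed, but a readout at month 19 to 21 is evidently not the current course.

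**Conclusion.** No change is needed. Under one reading the durations yield 98 to 108 events and a 75th event 6 to 8 months before month 27; under the other they yield 73 to 81 events and agree with the target. Both ranges rest on exponential event times and on my readings of the 10% dropout; the first also needs uniform accrual. Whichever reading was meant, the test, its levels, the 75 events and about 80% power are the same, so the plan followed as written gives a valid primary result.

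Restating the sentence would define a planning term and print expected dates that depend on an accrual pattern the documents do not give; it would alter no analysis. The rule that waits for 12 months after the last randomisation is a genuine trade-off. It buys more mature secondary data at the price of a later readout and a change to an event trigger stated consistently in both documents. Those secondary endpoints carry no multiplicity adjustment and are to be read descriptively (SAP 7.1), so no powered claim depends on the 12 months. A statistician can reasonably keep the trigger as it is.

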### **Subject Populations:**

#### Intent-to-Treat Population:

The Intent-to-Treat (ITT) population is defined as all subjects who were randomized in this study. The ITT population will be analyzed by treatment arm as randomized (i.e., treatment arm based on randomization assignment). The ITT population will be used to conduct efficacy analyses. For the ORR, only subjects with measurable disease at baseline will be included in the analysis.

#### Safety Population:

The safety population is defined as all randomized subjects who received at least 1 dose of study drug. The safety population will be analyzed by treatment arm as treated (i.e., based on the treatment the subject actually received rather than the treatment to which the subject was randomized). The safety population will be used to conduct safety analyses.

### **Efficacy:**

#### Primary Endpoint

- *Time to PSA progression:* PSA progression is defined as a  $\geq 25\%$  increase and an absolute increase of  $\geq 2 \mu\text{g/L}$  (2 ng/mL) above the nadir (i.e., lowest PSA value observed post baseline or at baseline), which is confirmed by a second consecutive value at least 3 weeks later. (Prostate Cancer Clinical Trials Working Group 3 criteria) (tested by central laboratory)

#### Secondary Endpoints

- *rPFS:* Defined as the time from randomization to the first objective evidence of radiographic disease progression as assessed by the investigator or death (defined as death from any cause within 24 weeks from study drug discontinuation), whichever occurs first.
- *Time to first SSE:* Defined as the time from randomization to the occurrence of the first SSE. SSE is defined as radiation or surgery to bone, clinically apparent pathological bone fracture or spinal cord compression.

- CONFIDENTIAL -

- *Time to castration resistance:* Defined as the time from randomization to the first castration-resistant event (radiographic disease progression, PSA progression or SSE), whichever occurs first.
- *PSA Response  $\geq 50\%$ , PSA Response  $\geq 90\%$ :* is defined as  $\geq 50\%$  and  $\geq 90\%$  reductions in PSA level from baseline to the lowest post-baseline PSA result as determined by the central laboratory, with a consecutive assessment conducted at least 3 weeks later to confirm the PSA response, respectively. The serum PSA response rate will be summarized at each time point. Waterfall plots of the rate of change from baseline will be constructed. PSA response  $\geq 50\%$  and  $\geq 90\%$  will be calculated by treatment group for subjects with PSA values at the baseline assessment and at least 1 post-baseline assessment.
- *Time to initiation of a new antineoplastic therapy:* Defined as the time from randomization to the initiation of antineoplastic subsequent to the study treatments.
- *PSA undetectable rate:* Defined as percentage of subjects with detectable ( $\geq 0.2$  ng/mL) PSA at baseline which become undetectable ( $< 0.2$  ng/mL) during study treatment.
- *ORR:* Defined as the percentage of subjects with measurable disease at baseline who achieved a complete or partial response in their soft tissue disease using the RECIST version 1.1 criteria on CT/MRI, and for bone lesions on bone scans.

